12.3.1.2 Serious Adverse Event

An SAE is defined as any untoward medical occurrence that:

- Results in death
- Is life-threatening
- Requires inpatient hospitalisation or prolongation of existing hospitalisation
- Results in persistent or significant disability/incapacity
- Is a congenital anomaly/birth defect
- Results in vision loss or is vision threatening
- Is an other important medical event(s).

The term 'life-threatening' in the definition of 'serious' refers to an event in which the subject is at risk of death at the time of the event. It does not refer to an event that hypothetically might cause death if it were more severe.

Hospitalisation for a pre-existing condition, including elective procedures, which has not worsened, does not constitute an SAE.

Other events that may not result in death, are not life threatening or do not require hospitalisation, may be considered an SAE when, based upon appropriate medical judgment, the event may jeopardise the subject and may require medical or surgical intervention to prevent one of the outcomes listed above.

Vision Loss to Be Reported as a Serious Adverse Event

Vision Loss NOT TO BE Reported as an SAE:

• Surgery-related BCVA decrease of ≥15 letters on ETDRS chart occurring within 1 day of surgery, but recovering / resolving at post-operative Days 7 and 14.

Vision Loss or Vision-Threatening Event TO BE Reported as an SAE:

- Surgery-related BCVA decrease of ≥15 letters on ETDRS chart that occurs within 1 day of surgery and that has not recovered* by the 1-Month Visit.
- A decrease in BCVA of ≥15 letters on ETDRS chart that occurs within 1 day of surgery, however, in the investigator's opinion:
 - Has an evolution not consistent with the expected post-operative course;
 - May be attributable to a complication that occurred during surgery, or another untoward event, or the study drug;
 - Actually or potentially requires any surgical or medical intervention to prevent permanent loss of vision.
- Non-surgery-related, sustained (>48 hours duration) decrease from baseline in BCVA of ≥15 letters on ETDRS chart.

*Recovery / Resolution of BCVA loss is defined as a return to baseline BCVA within 5 letters on the ETDRS chart.

12.3.2 Recording of Adverse Events

AEs/SAEs will be collected from the time the subject provides written informed consent through the EOS Visit (or ET Visit or Unscheduled Visits, if applicable).

Subjects will be questioned on the occurrence of an AE at every visit including any unscheduled visit, by using non-leading questioning such as 'How have you been since the last visit?' This will include the telephone contact at Visits 2, 3 and 4 for subjects in the Control group.

All AEs occurring during the study observed by the investigator or reported by the subject, whether or not attributed to study medication or the surgical procedure, will be recorded in the subject's medical records and in the eCRF.

The following information will be recorded in the eCRF for each AE: description, date of onset and end date, outcome, severity, assessment of relatedness to study medication/study procedure, the action taken and confirmation of whether the event is considered serious (see Section 12.3.1.2 for the definition of seriousness). Follow-up information should be provided as necessary (see Section 12.3.3 for specifics on follow-up procedures).

AE severity and relationship to the study medication or the surgical procedure will be assessed at the site by the investigator or a medically qualified designee.

AE Severity

The severity of events will be assessed on the following scale:

1 =mild (awareness of sign or symptom, but easily tolerated)

2 = moderate (discomfort sufficient to cause interference with normal activities)

3 = severe (incapacitating, with inability to perform normal activities).

AE Relationship

When assigning relatedness of the AE, consideration will be given to whether there is a plausible relationship to either the study medication or the surgical procedure. The following are definitions of relatedness that will be used in this study.

| Unrelated: | It is not reasonably related in time to the administration of the study medication/surgical procedure or exposure of the study medication/surgical procedure has not occurred |
|------------|--|
| Related: | A reasonable possibility exists that the study medication / study procedure caused the AE. A suspected AE can be further defined by: |
| | Possibly related: clinically or biologically reasonable relative to the administration of the study medication/surgical procedure, but the event could have been due to another equally likely cause |
| | Probably related: is clinically/biologically reasonable relative to the administration of the study medication/surgical procedure, and the event is more likely explained by exposure to/administration of the study medication/surgical procedure than by other factors and causes |

Definitely related: a causal relationship of the onset of the event, relative to administration of the study medication/surgical procedure exists and there is no other cause to explain the event.

When a relationship is determined to exist, the investigator or medical designee will further define if that relationship is to the *study medication*, the *study procedure*, *both*, or *unknown*.

12.3.3 Follow-up of Adverse Events

AEs will be followed until the subject has recovered or the subject's participation in the study is complete.

Subjects who are withdrawn from the study as a result of a drug-related AE will be followed up until the event has resolved, subsided, stabilised, or the subject withdraws consent or is lost to follow-up.

All SAEs, regardless of attribution to study medication or the surgical procedure, should be followed-up until the event has resolved, subsided, stabilised, or the subject withdraws consent or is lost to follow-up. The Sponsor (or designee) will follow up SAE reports to completion. Investigators are expected to provide the requested additional information for a complete assessment and documentation of the SAE reports within a timely manner.

12.3.4 Reporting of Serious Adverse Events

The investigator shall immediately (within 24 hours of learning of the event) report any SAE to the Sponsor (or its designee) by completing and emailing an SAE form. The initial report shall be promptly followed up with a more detailed report providing specifics about the subject and the event. Copies of hospital reports, autopsy reports, and other documents should be provided (if applicable).

The sponsor may unmask any SAE reports that are serious, unexpected, and related to the study drug, as required, in accordance with safety reporting guidance and regulations.

The Sponsor will report SAEs and Suspected, Unexpected, Serious Adverse Reactions (SUSARs) to investigative sites, IRBs/IECs and regulatory authorities in compliance with current legislation. All cases that are fatal or life-threatening will be reported immediately after the Sponsor received the initial report from the Investigator. All non-fatal or non-life-threatening cases will be reported within a maximum of fifteen days after the initial Investigators report. The Sponsor will also provide periodic safety reports to IRBs/IECs and regulatory authorities as applicable. Follow-up SAE reports will be submitted within 15 days of receiving the information.

A sample SAE form is provided in the Study Operations Manual, along with the SAE reporting contact information.

12.3.5 **Procedures for Unmasking**

The Investigator has the ability to unmask an individual subject's treatment assignment in order to provide emergency treatment. Unmasking is appropriate when knowledge of the subject's dose would affect the medical management of the subject.

If the Investigator determines unmasking is required, then s/he unmasks the subject through the Electronic Data Capture (EDC) system, files the resulting confirmation in a restricted file

until the end of the study, and notifies the Medical Monitor within 24 hours that the subject's treatment assignment has been unmasked. The Investigator will not communicate the treatment assignment to the Medical Monitor or to any sponsor or study team staff; nor should the treatment assignment be communicated to site staff other than those personnel who require that knowledge in order to treat the subject.

The Investigator will ensure that the rationale, date, and time of unmasking is noted in the subject's source documentation, but not the treatment assignment. The medical emergency that necessitated unmasking must also be recorded in the source documentation and the case report form per standard study procedures.

12.3.6 Data Monitoring Committee

An independent Data Monitoring Committee (DMC) will be used in this study to safeguard the safety and interests of study subjects and assess the safety and risk/benefit of the gene therapy intervention during the trial.

At regular intervals during the study, the DMC will review the progress and accrued study data. The DMC will inform the Sponsor if there is a consensus that the ongoing data show that the gene therapy, its method of administration, and/or the study design are no longer in the best interests of study subjects. Details of DMC organisation and responsibilities are included within a DMC charter that has been approved by all committee members.

12.4 Pregnancy

Any pregnancy that occurs during the clinical study in a female partner of a study subject should be recorded on a Pregnancy Notification Form. Subject consent is required prior to the collection of personal data, however, the investigator shall immediately (within 24 hours of learning of the event) report the pregnancy, with at least preliminary data, to the Sponsor (or its designee) by completing and emailing the Pregnancy Notification Form. In addition, if possible, outcome of the pregnancy fathered by the subject should be recorded, including any congenital abnormality or birth defect.

12.5 Laboratory Assessments

12.5.1 Immunogenicity

For the evaluation of immunogenicity, blood will be collected at the times indicated in Table 3. Select samples may be analysed.

Immunoassays are planned to assess antibody and cell-based responses against AAV2-REP1. Immunoassays may or may not be conducted on these samples, depending on safety findings from Investigator Sponsored studies and ongoing NighstaRx sponsored studies with AAV2-REP1. If immunoassays are conducted, ELISPOT assays will be used for T-cell mediated immune responses to transgene, and antibody responses will be assayed using ELISA- and cell-based methods.

All immunogenicity samples will be sent to a central laboratory for analysis. Refer to the Study Operations Manual for details on the shipping and handling of samples.

Remaining samples may be stored for up to 15 years or per local regulations.

12.6 Vital Signs

Vital signs (pulse and systolic and diastolic blood pressure) will be taken at the times indicated in Table 3.

Vital signs should be taken after the subject is seated for at least 5 minutes.

13 STATISTICAL CONSIDERATIONS

Details of the statistical analyses will be described separately in the STAR Statistical Analysis Plan.

13.1 Sample Size

Approximately 160 subjects will be enrolled in the study (64, high dose group; 32, low dose group; 64, control group).

The sample size calculation is based on a Fischer's exact test. CHM is a degenerative disease, it is therefore assumed that a \geq 15 letter BCVA gain would not be observed in subjects without CHM treatment. Assuming that 16.7% of the treated subjects will gain \geq 15 letters BCVA at Month 12, 56 subjects in the high dose group and the control group provide at least 90% power at a 0.05 level of significance with a 2-sided test. To be conservative, 64 patients in the high dose group and 64 patients in the control group is needed to ensure 85% power in case 1 patient in the untreated control group has \geq 15 letter BCVA gain by chance, which corresponds to a total of 160 patients completing the study.

13.2 Procedure for Accounting for Missing Data

All reasonable efforts will be made to obtain complete data for both eyes on all subjects. However, missing observations may occur. Management of dropout and missing observations will depend on their nature and frequency.

For binary efficacy endpoints (including the primary efficacy endpoint), missing data will be imputed as failure, to be conservative. For the continuous efficacy endpoints, the last observation carried forward (LOCF) approach will be utilized for handling missing data.

To evaluate the robustness of the results of the main analyses, sensitivity analyses of the primary and secondary endpoints will be performed. These analyses will include different imputation methods on different analysis sets and will be described in detail in the Statistical Analysis Plan.

Safety data will be analysed on observed data. Missing data will not be imputed.

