The rationale for including alternative data ascertainment, especially out of window visits in the primary analysis is the following: 1) It is in line with FDA and EMA guidance (U. S. Food and Drug Administration 2020, EMA 2020) on handling analysis during COVID-19 pandemic; 2) No further improvement in the treated patients is expected after the initial response around roughly 1-3 months, if any, post one-time injection of this gene therapy. Therefore, including the out of window visit, especially the visits beyond Month 12 scheduled window for the treated patients is considered a conservative approach considering potential trend of natural disease progression in the long-term follow up; 3) Very slow progression is expected in untreated control patients. The natural history study NIGHT showed an average of 0.5 letters of vision loss in untreated patients during 20 months follow up. Therefore, minimum impact on the analysis is expected from the usage of visits a few months post protocol defined window for the untreated patients, especially for the primary endpoint proportions of >= 15 letters increase from the baseline in BCVA.

Sensitivity analysis will be performed on the primary endpoint and the key secondary endpoints if applicable. The main analyses described in Section 10.1 and Section 10.2 will be repeated as follows:

- On the ITT population excluding subjects who withdraw from the study or died due to COVID-19 without any imputations, but include data collected by alternative ascertainment approaches.
- On the ITT population, where assessments performed at local non-study sites are replaced by the ad-hoc visit assessment (where available), irrespective of the interval between the ad-hoc visit and the local non-study site visit.
- On the ITT population, multiple imputation based on missing at random (MAR) will be applied to impute the data collected by alternative ascertainment approaches with Month 12 visit more than 2 months prior or 3 months after the protocol defined visit window or data missing from early termination or death due to COVID-19. In this

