analysis, with extra scientific rigor, multiple imputation will also be applied to Month 12 BCVA collected more than 2 months prior or 3 months after the visit window not due to COVID-19. Assuming the BCVA at different visits follows a multivariate normal distribution, the Monte Carlo Markov Chain (MCMC) will be implemented to impute all missing data and the Month 12 BCVA collected more than 2 months prior or 3 months after the visit window (Schafer 1997, Schafer 1999). Each imputed data for continuous endpoint, analysis of covariance (ANCOVA) model including surgical group, baseline value of the assessment, and study arms will be applied. For binary endpoint, the proportion difference and the corresponding standard error between the treatment groups (i.e. high dose vs. placebo, low dose vs. placebo) will be calculated for each imputed dataset using the two-sample Binomial test. Analysis will be performed for each of the 100 imputed datasets and results will be combined by Rubin's rule (Rubin 1976, Rubin 1987) for inference assuming the statistics estimated from each imputed dataset are normally distributed. The Sample SAS code is in Appendix 4.

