10.2 Key Secondary Endpoints

The three key secondary endpoints and the corresponding primary analysis are as summarized and presented by pre-specified order in Table 1.

Biogen /	NightstaRx, Ltd
BIIB111	

The continuous efficacy endpoint will be analyzed by the analysis of covariance (ANCOVA) model including surgical group, baseline value of the assessment, and study arms. Missing data will be handled by the last observation carried forward (LOCF) approach.

The binary efficacy endpoints will be analyzed with the same method used for the primary efficacy endpoint with missing values imputed as failure.

The least square (LS) means, standard error (SE) and 95% CI will be reported for each treatment at each post-randomization visit. Least square mean, SE, 95% CI, and p-value for the between group differences will also be provided.

The primary analysis of the key secondary endpoints will be based on the ITT population, and supportive analyses will be performed based on the PP population and the randomized population. When performing the supportive analysis based on the randomized population, for subjects who do not have any post-baseline assessments, the baseline will be used when LOCF approach is applied (i.e. the change from baseline will be zero). Knowing the patients who had BCVA below 34 ETDRS letters at Month 12 for study eye, if any, will at site not be the responders of subjects with a ≥ 10 -letter improvement from Baseline in BCVA at Month 12, these subjects with minor protocol deviation will be included in the supportive analysis of the secondary endpoint of Proportion of subjects with a ≥ 10 -letter improvement from Baseline in BCVA at Month 12 measured by the ETDRS chart based on the PP population. When performing the supportive analysis based on PP population for the secondary endpoints of (a) Change from Baseline in BCVA at Month 12 measured by the ETDRS chart and (b) Proportion of subjects with no decrease from Baseline in BCVA or a decrease from Baseline in BCVA of <5 ETDRS letters at Month 12 measured by the ETDRS chart, subjects at site who had BCVA below 34 at Month 12 will be excluded from these analyses. The background information for site is described in Section 8.

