Additional supportive analysis will be conducted by comparing the study eyes vs. the fellow eyes (i.e., contralateral control) within the low dose and the high dose treatment groups. The binary efficacy endpoints will be analyzed at the Month 12 visit using the paired McNemar test. Change from baseline in BCVA at Month 12 will be compared between the study eye and the fellow eye using the linear mixed model where the two eyes are considered correlated within each patient. The model will contain the variables for baseline BCVA, treatment groups (low dose and high dose), surgical group, eye (study eye vs fellow eye) and the treatment*eye interaction, where the eye variable acts as the repeat variable. (See sample SAS code in Appendix 5).

	Key Secondary Endpoint	Statistical Method
1	Change from Baseline in BCVA at Month 12 measured by the ETDRS chart	ANCOVA
2	Proportion of subjects with a ≥10-letter improvement from Baseline in BCVA at Month 12 measured by the ETDRS chart	Fisher's Exact Test; Fisher's Exact-Boschloo test with a Berger-Boos correction of beta=0.001; CMH Approach
3	Proportion of subjects with no decrease from Baseline in BCVA or a decrease from Baseline in BCVA of <5 ETDRS letters at Month 12 measured by the ETDRS chart	Fisher's Exact Test; Fisher's Exact-Boschloo test with a Berger-Boos correction of beta=0.001; CMH Approach

Tabla 1	Statistical Tests	for Vor	Secondamy	Efficient	Endnointe
Table 1	Statistical Lesis	IUI KEY	Secondary	Efficacy	Enapoints

Biogen / NightstaRy	x, Ltd
BIIB111	

Abbreviations: BCVA= best corrected visual acuity, CHM= choroideremia, ETDRS=Early Treatment of Diabetic Retinopathy Study

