13 DROP OUT PROFILE

The number, pattern and timing of missing data will be examined by treatment group along with the reasons for withdrawal or for missing data.

The pattern of missing data due to discontinuation will be characterised by summarising the time to discontinuation based on the Kaplan-Meier estimates and the corresponding Kaplan-Meier curves. Time to discontinuation is calculated as the date of discontinuation – date of Visit 2 (i.e., surgery or phone contact) + 1.

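### Key secondary 3 (loss under 5 letters): counting missing as failure is not guaranteed to be conservative, and no planned analysis varies the missing-data assumption by arm

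*Protocol*

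**What the plan says.** Protocol 13.2 sets one rule for every binary endpoint and gives the reason: "For binary efficacy endpoints (including the primary efficacy endpoint), missing data will be imputed as failure, to be conservative". SAP 10.2 repeats the rule for the key secondaries without the reason: "The binary efficacy endpoints will be analyzed with the same method used for the primary efficacy endpoint with missing values imputed as failure". Key secondary 3 is the proportion of subjects with no loss of BCVA, or a loss under 5 letters, at Month 12. Under SAP 10.3 it is tested last, after the primary endpoint and the other two key secondaries.

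On the expected course without treatment, SAP 5.5 says: "The natural history study NIGHT showed an average of 0.5 letters of vision loss in untreated patients during 20 months follow up".

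Planned analyses that bear on missing data for this endpoint:
- **SAP 10.4.1:** LOCF for the binary endpoints, on the ITT population.
- **SAP 5.5:** a missing-at-random multiple imputation with a binary version, in which "the Monte Carlo Markov Chain (MCMC) will be implemented to impute all missing data". The section opens with: "Sensitivity analysis will be performed on the primary endpoint and the key secondary endpoints if applicable".
- **SAP 10.2:** "supportive analyses will be performed based on the PP population and the randomized population". No other rule for missing binary values is stated for these populations.
- **SAP 10.2:** a paired test "comparing the study eyes vs. the fellow eyes (i.e., contralateral control) within the low dose and the high dose treatment groups".
- **SAP 13:** "The number, pattern and timing of missing data will be examined by treatment group".

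The MMRM (SAP 10.4.2) and the control-based imputation (SAP 10.4.3) are limited to the continuous change in BCVA.

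**The concern.** Calling missing a failure leans against treatment when success is rare in controls. That fits the 15-letter and 10-letter gain endpoints. Key secondary 3 is the reverse: standing still is success, and the SAP expects controls to change very little. The rule then penalises whichever arm has more missing data.

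This is the endpoint that would support a claim of preserved vision. A reader of Protocol 13.2 would take it that the main analysis already leans against treatment. If controls miss Month 12 more often, it leans the other way, and no planned table shows how many missing controls would have to be stable before a significant result is lost.

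A smaller matter concerns LOCF. No earliest visit is set. Treated subjects have Day 1 and Day 7 BCVA from unmasked assessors (Protocol 9.6.1), while controls have only telephone contacts until Month 1 (Protocol Table 3, footnote b). Only a treated subject can therefore have an early post-operative score carried to Month 12.

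**Working it through.** **1. The plan's own figures.** Protocol 13.1 gives power only for the primary endpoint. Exact enumeration of the two-sided Fisher test gives 92.3% for 56 per arm at 16.7% vs 0% (stated: at least 90%), and 85.9% for 64 per arm with exactly one control responder (stated: 85%). Both agree. No rate, power or missing-data figure is given for key secondary 3.

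**2. Direction of the rule.** Let m be the missing rate and s the true success share, with missingness unrelated to outcome; t is treated and c is control. Recorded success is s(1 - m), so

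recorded difference = s_t(1 - m_t) - s_c(1 - m_c) = (s_t - s_c) + (m_c s_c - m_t s_t).

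The rule favours treatment when m_c s_c > m_t s_t. With equal shares the shift is s(m_c - m_t); at s = 90% and 5%/10% missing it is 0.90 x 0.05 = 4.5 points. With unequal shares, break-even is m_c = m_t s_t / s_c. For 10% treated missing that is 0.10 x 0.90/0.80 = 11.3%, or 0.10 x 0.80/0.90 = 8.9%.

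For contrast, the 15-letter endpoint at a 1/64 response in both arms and 5%/20% missing shifts by (1/64) x 0.15 = 0.2 points. There the rule does no harm.

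**3. Size.** Inputs from the documents: 64 per arm (Protocol 13.1) and two-sided Fisher at 0.05 (Protocol 13.6, SAP 10.1). Assumed: the missing rates, and a common stable share of 80, 90 or 95%. The table gives the exact chance of p < 0.05 in favour of treatment when there is no true difference (nominal 2.5%), taking key secondary 3 on its own.

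| Missing treated / control | s = 80% | s = 90% | s = 95% |
|---|---|---|---|
| 5% / 5% | 1.5% | 1.4% | 1.1% |
| 5% / 7% | 2.5% | 2.8% | 2.8% |
| 5% / 8% | 3.2% | 3.8% | 4.1% |
| 5% / 10% | 5.0% | 6.5% | 7.9% |
| 10% / 3% | at most 0.2% | at most 0.2% | at most 0.2% |

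Because the endpoint is tested last, the chance that the whole sequence ends in a false win here cannot exceed these figures.

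**4. A tipping case (invented counts).** Suppose 57 of 61 observed treated and 47 of 58 observed controls are stable, with 3 and 6 missing.
- Missing = failure: 57/64 vs 47/64, p = 0.040.
- One missing control counted as stable: 57/64 vs 48/64, p = 0.064.
- All 3 missing treated and 5 of 6 missing controls counted as stable, close to the observed rates: 60/64 vs 52/64, p = 0.059.

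**5. What the planned LOCF check would catch.** If carried values equal the true Month 12 values, a win that must hold under both missing = failure and LOCF has a false-win chance of between about 0.4% and 1.2% at 5%/10% missing.

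**6. Early values in LOCF.** One affected subject moves a 64-subject arm mean by 10/64 = 0.16 letters per 10 letters carried, and the key secondary 3 proportion by at most 1/64 = 1.6 points.

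**The case against.** A reader might infer that nothing planned would show whether a win on key secondary 3 survives unequal missingness. The documents do not support that. ITT entry requires a post-treatment BCVA (SAP 7.3), so every ITT subject has a value to carry, and the LOCF check in SAP 10.4.1 removes the failure rule altogether. The imputation in SAP 5.5 replaces it too, with treatment arm in the model, and its conditional wording need not mean that key secondary 3 is skipped. Protocol 13.2 itself promises sensitivity analyses with other imputation methods. All of this stands. What remains is narrower: these analyses apply one assumption to both arms, and the imputation sits in a COVID-19 section with conditional reach.

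A reader might also infer that controls did, or will, miss Month 12 more often. No document shows this. Controls know their assignment and receive no treatment, which makes it possible. The one disposition figure, 3 of 83 randomised who left before Visit 2, is not split by arm and concerns subjects outside ITT.

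The ITT definition is a partial offset. A control who leaves before any BCVA is dropped, while a treated subject who leaves after Day 1 stays in and counts as a failure. The calculations hold 64 per arm and do not credit this. The offset does not apply in the randomised-population analysis.

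**Conclusion.** The concern holds in limited form. The statement that missing = failure is conservative is not assured for key secondary 3: it depends on which arm has more missing Month 12 data, weighted by that arm's success share. An excess of 2 to 3 points in controls leaves the error near nominal (2.5-4.1%). At twice the treated rate (5%/10%) it reaches 5.0-7.9%. With more missing in the treated arm the rule is strongly conservative. These figures rest on assumed missing rates and stable shares, missingness unrelated to outcome, and no true difference.

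The planned LOCF and imputation would reveal much of any distortion; the gap is the absence of an analysis that varies the assumption by arm. The LOCF visit rule is a minor point: few subjects should be affected, and the likely bias is against treatment. The point is worth correcting before any claim on this endpoint, but it does not threaten the primary result.

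**What to change.** 1. Keep missing = failure as the main rule for key secondary 3. In Protocol 13.2, limit the word conservative to the 15-letter and 10-letter gain endpoints.
2. State that the SAP 5.5 / Appendix 4 imputation will be run for key secondary 3 for all missing Month 12 BCVA, using visits that both arms have: baseline and Months 1, 4, 8 and 12. The sample code lists five post-baseline visits, while controls have four.
3. Add one tipping-point table that varies, separately by arm, how many missing subjects count as stable. Show it with the SAP 13 summary of missing data by arm.
4. In the LOCF analyses, carry only BCVA from Month 1 onward. In the binary check (SAP 10.4.1), count a subject with no such value as a failure.
5. For key secondary 1 in ITT, report how many treated subjects have only Day 1 or Day 7 BCVA. Show the result with those values carried and with those subjects left out, as a sensitivity analysis without a new decision rule.

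The cost is a little more analysis work and edits to Protocol 13.2 and SAP 5.5, 10.2, 10.4 and Appendix 4. The main test of key secondary 3, the sample size and the visits do not change.
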